6.3 Data Analysis

A table of outcome measures recorded during the study can be found in Appendix. Scores rating daily 491 492 average, worst, and least pain will be compared between groups. Changes in pain will be evaluated for

individual subjects and compared between groups. For each subject, mean pain scores over the first and 493

494 second months following TFA or TTA surgery will be calculated. An overall mean across all subjects will

be calculated. Additionally, sub-analyses will be performed to determine if there is a difference in these 495

outcomes between groups over different post-operative phases (such as acute (e.g. days 1-30) or subacute 496

497 (e.g., 1-3 months), or chronic (e.g. >3 months)). Statistical analysis will be performed with two-sample t-

498 test, and p-values will be reported without adjustment, consistent with feasibility study design and the

499 number of subjects.

500 Pain medication usage will be recorded in subject diaries and obtained during follow up encounters. Opioid

medication use will be analyzed by averaging 24-hour morphine equivalent dosing (MED) over each 501

502 follow-up interval and comparing groups. Changes in opioid medication use will be reported for individual

503 subjects by calculating morphine equivalent dosing (MED). Average MED will be calculated and compared between groups. The time to cessation of opioid use will be reported. Side effects associated 504

with opioid use will be assessed at each visit and the number of side effects occurring over various intervals 505

506 will be recorded. Analgesic-related outcomes will be compared between the Groups.

507 Patient Global Impression of Change (PGIC), Pain Catastrophizing Scale (PCS), and Pain Disability Index

508 (PDI) scores will be averaged for each group and compared. Data regarding functional outcomes

509 (Functional Independence Measure [FIM] score), time to wound healing, incidence of neuromas, prosthesis

fitting, time to hospital discharge, 30-day readmission rate, and hospital discharge survey will be compared 510

between groups. 511

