1.2 Objectives

- 14 The goal of this study is to demonstrate that PNS is a safe, effective method of reducing acute and chronic
- pain in the nontraumatic lower extremity amputee, and can lessen the use of opioid pain medications. This
- pilot study will evaluate the feasibility of recruitment, randomization, retention, assessment procedures,
- and implementation of PNS in the acute post-operative period to develop a larger, multicenter, blinded,
- placebo-controlled, randomized clinical trial to evaluate efficacy in reducing acute and chronic PLP and
- 19 RLP. Upon completion, we will assess the reliability and validity of the proposed study design. In
- 20 conducting this investigation, we hope to answer the following questions:
 - What is the feasibility of placing a PNS system in a transfemoral or transtibial amputee in the acute post-operative period?
 - Does PNS produce clinically significant reductions in acute PLP or RLP?
 - Does the application of PNS in the acute post-operative period reduce the incidence and severity of chronic PLP and RLP?
 - Can PNS lessen the use of opioid and non-opioid pain medications?
- Does PNS affect time to prosthesis fitting, function outcomes (Functional Independence Measure [FIM] scores), wound healing, incidence of neuromas, time to hospital discharge, 30-day readmission rate, and hospital discharge survey answers?

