3.2 Study Design

- This prospective randomized controlled trial aims to assess the feasibility of using a novel percutaneous
- peripheral nerve stimulator system to produce clinically significant reductions in acute post-surgical pain
- after nontraumatic lower extremity amputation, and evaluate reductions in the incidence and/or severity of
- chronic PLP or RLP. Subjects who have moderate pain 2 to 7 days after transfemoral or transibial
- amputation surgery will be enrolled and randomized to Group 1 ("Treatment Group") or Group 2 ("Control
- Group"). Subjects in Group 1 will be treated with 30 to 60 days of PNS in addition to SMT. Subjects in
- Group 2 will be treated with the SMT alone. SMT is defined as the same routine medical care given to all
- patients, regardless of whether they are enrolled in the study. This may include, but is not limited to non-
- opioid and opioid pain medications, regional anesthesia peripheral nerve blockade, daily postoperative
- visits by the Acute Pain Service, and follow-up appointments in the Interventional Pain Clinic.
- Group 1: 30 to 60 days of peripheral nerve stimulation starting within 7 days after surgery and Standard Medical Therapy
 - Group 2: Standard Medical Therapy only
- Subjects are evaluated daily by study investigators from the time of study enrollment to hospital discharge.
- 30 Subsequent telephone or outpatient clinic evaluations occur at intervals which are detailed in the Schedule
- of Study Procedures (Appendix).

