5.5.1 Visit 1: 24-48 hours after removal of peripheral nerve block catheter

Subjects will be assessed at least 24-48 hours after removal of the peripheral nerve catheter (or after the effects of a single shot femoral and/or sciatic nerve block have worn off). They will be evaluated for post-surgical complications, and for the presence of phantom limb sensation or pain and RLP. Average pain severity and anatomic distribution will be reported by answering BPI-SF #2 and #5.

Subjects in Group 1 will proceed to Visit 2 and undergo placement of the peripheral nerve stimulator lead(s) by post-op day 7, in addition to receiving SMT. Subjects in Group 2 will skip to Visit 3. They will be treated with SMT and followed up by study investigators daily until discharged. They will subsequently be followed up by telephone according to the Schedule of Study Procedures.

5.5.2 Visit 2A: Placement of percutaneous peripheral stimulator leads (Group 1

only)

Subjects randomized to Group 1 proceed to placement of the stimulator leads by post-op day 7 to begin peripheral nerve stimulation therapy with the SPRINTTM PNS System (Figure 2.1). The procedure for placement of the peripheral nerve stimulator lead (Figure 2.2) is similar to placement of a peripheral nerve catheter for local anesthetic blockade. The main difference is that instead of delivering medications, electrical stimulation is applied to the peripheral nerve over a wide range of parameters. Also, the stimulator lead does not need to be placed as close to the nerve as a local anesthetic peripheral nerve catheter. This study will evaluate the application of one or two leads per subject: one for the femoral nerve and/or one for the sciatic nerve. Lead placement is expected to take up to 2 hours.

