5.5.4 Visits 3, 4 and 5: Weekly telephone follow-up evaluations

Visits 3, 4 and 5 consist of weekly telephone evaluations at 1, 2 and 3 weeks after starting peripheral nerve stimulation (Group 1) or discontinuation of peripheral nerve block (Group 2). If issues related to the peripheral nerve stimulator device or leads occur and cannot be resolved by telephone, subjects may be evaluated in the Interventional Pain Clinic as needed.

Subjects are asked to rate their worst, least, and average PLP and RLP (BPI #3, #4, and #5). A medical reconciliation will be completed during each phone evaluation by asking the subject how many pills of narcotic pain medications they have left and querying the Virginia Prescription Monitoring Program Database.

5.5.5 Visit 6: First outpatient clinic evaluation / 30 days after start of PNS

All subjects are asked to return to the Interventional Pain Clinic at 4 weeks after the start of peripheral nerve stimulation. Stimulator devices (Group 1) will be inspected to ensure appropriate function. Lead exit sites are inspected for skin irritation, infection, and inflammation. Maintenance, care of the leads and lead exit sites, and bandage changes will be performed as needed.

All subjects are asked to rate their worst, least, and average PLP and RLP (BPI #3, #4, and #5). Subjects will rate the degree with which pain has interfered with general activity, mood, walking ability, sleep, and enjoyment of life (BPI #9). Pain Disability Index (PDI) and Patient Global Impression of Change (PGIC) will be assessed. A medical reconciliation will be completed during each phone evaluation by asking the subject how many pills of narcotic pain medications they have left and querying the Virginia Prescription Monitoring Program Database.

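### The first-month pain mean is counted from surgery, so it includes pain scored before stimulation starts, and the plan does not say which scores enter or how daily and weekly scores are weighted

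*Combined protocol and SAP*

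**What the plan says.** Section 6.3 builds the monthly summary in one sentence. It begins "For each subject, mean pain scores over the first and" and continues "second months following TFA or TTA surgery will be calculated". The same section says that scores for "average, worst, and least pain will be compared between groups", and it plans sub-analyses of "outcomes between groups over different post-operative phases (such as acute (e.g. days 1-30) or subacute". All these windows start at the operation. No rule lists the assessments that enter, leaves out scores taken before treatment, or sets weights.

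Treatment starts later. Section 5.5.2 states: "Subjects randomized to Group 1 proceed to placement of the stimulator leads by post-op day 7". Section 5.5.1 places Visit 1 before that step, 24-48 hours after nerve-block removal. Average pain is recorded there, and the Schedule of Study Procedures labels the visit as baseline.

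The frequency of assessment changes at discharge. Section 3.2 says "Subjects are evaluated daily by study investigators from the time of study enrollment to hospital discharge", and Section 5.5.3 includes least, worst and average pain in the daily inpatient evaluation. After that, "Visits 3, 4 and 5 consist of weekly telephone evaluations at 1, 2 and 3 weeks after starting peripheral nerve" stimulation in Group 1, or after block removal in Group 2 (Section 5.5.4). Section 5.5.3 expects a stay of about 14 days for transfemoral amputation. Section 1.2 lists "wound healing, incidence of neuromas, time to hospital discharge, 30-day readmission rate" among the outcomes that PNS might affect, and Section 6.3 compares time to discharge between groups.

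**The concern.** There are two separate problems, both in the first month.

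- **Dilution.** A score taken before PNS starts has the same expected value in both arms. Averaging it into the outcome shrinks the between-group difference in proportion to its share of the scores.
- **Weights set by discharge.** If every recorded score counts equally, a subject contributes one score per day in hospital and one per week at home. Two subjects with the same pain course then get different means if they leave hospital on different days. Time to discharge is itself compared between the groups, so the weighting could differ by arm.

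The trial is a pilot whose results are meant to shape a larger one (Section 6.1). The practical risk is a planning estimate that is too small, or that is shifted by discharge timing.

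**Working it through.** The plan gives no effect size, standard deviation or weighting rule, so it has no figure of its own to reproduce. I counted scores by post-operative day.

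**Inputs from the protocol:** PNS by day 7 (5.5.1, 5.5.2); block catheter usually out by day 5 (5.5), which puts Visit 1 at about day 6-7; stay about 14 days, with Group 1 discharge 7-14 days after PNS start (5.5.3), so day 14-21 if PNS starts on day 7; calls 1, 2 and 3 weeks after PNS start (5.5.4), so days 14, 21 and 28.

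**Assumptions:** month 1 is days 1-30 and month 2 is days 31-60; scores have equal weight; PNS starts on day 7 unless stated; a call that falls during the stay is not counted twice. A constant true effect of 2 points from PNS start is used for illustration.

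**Step 1: dilution.** Share = pre-PNS scores / all month-1 scores. Apparent effect = 2 x (1 - share).

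| Scores taken to enter | Count | Share | 2 points appears as |
|---|---|---|---|
| Visit 1, daily on PNS, calls; discharge day 14 | 1/(1+7+2) = 1/10 | 10% | 1.80 |
| Same, discharge day 21 | 1/(1+14+1) = 1/16 | 6% | 1.88 |
| Visit 1 on day 6, day 7 counted as on PNS; discharge day 14 | 1/11 | 9% | 1.82 |
| Scheduled visits only (Visit 1; days 14, 21, 28) | 1/4 | 25% | 1.50 |
| Daily from day 1, PNS day 6, that day counted as on PNS; discharge day 14 | 5/16 | 31% | 1.38 |
| Daily from day 1, PNS day 7, that day counted as on PNS; discharge day 14 | 6/16 | 38% | 1.25 |
| Daily from day 1, PNS day 7, that day counted as before PNS; discharge day 14 | 7/16 | 44% | 1.13 |

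**Step 2: length of stay.** Assume no treatment effect, Visit 1 on day 6, daily scores from day 6 to discharge, and calls on days 14, 21 and 28. The curves are assumptions, not trial data:

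- linear: P(d) = 6 - 3(d - 1)/29
- exponential: P(d) = 2 + 5 x 0.5^((d - 1)/h), with h = 7 or 5 days

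The plain mean of the recorded scores, by discharge day (number of scores in brackets), is:

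| Curve | Day 10 (8) | Day 12 (10) | Day 16 (13) | Day 21 (17) | 12 v 16 | 10 v 21 |
|---|---|---|---|---|---|---|
| Linear | 4.77 | 4.80 | 4.75 | 4.62 | 0.05 | 0.15 |
| h = 7 | 3.88 | 3.86 | 3.73 | 3.53 | 0.13 | 0.35 |
| h = 5 | 3.36 | 3.32 | 3.20 | 3.02 | 0.13 | 0.35 |

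Differences were taken before rounding. Every subject on a given curve has identical pain, so the shifts come only from the weights.

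**Step 3: month 2.** The 4-week clinic visit and the calls at 5, 6 and 7 weeks fall on days 35, 42, 49 and 56. None of these 4 scores precedes PNS, and all are weekly for any discharge by day 30. There is no dilution and no length-of-stay weighting.

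**Step 4: is time-weighting enough?** No. With scores from day 1, a time-weighted mean that still starts at surgery leaves 7/30 = 23% of the window before PNS. Both the start of the window and the weights need attention.

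**The case against.** The strongest reply is that the plan never says that daily and weekly scores are pooled. Section 5.5.3 refers the inpatient pain items to the Schedule of Study Procedures, which, as far as it can be read, has no daily inpatient column. If only scheduled visits count, length of stay has no influence on the weights. This stands: equal-weight pooling is the natural reading of Sections 5.5.3 and 6.3, but it is not stated. The scheduled-visits reading does not rescue the mean, however, because Visit 1 is then one score in four.

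Second, a reader might infer that a third or more of the first-month scores precede treatment. The documents do not support that as the expected case. Before Visit 1 they mention only daily acute pain service evaluations and name no pain item for them. Subjects may also enrol as late as catheter removal, so day-1 scores cannot exist for everyone. The 31-44% range is an upper bound.

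Third, a reader might infer that the plan expects PNS to shorten the stay. Section 1.2 only asks whether PNS affects time to discharge, and the hypothesis in Section 1.3 does not mention it. An 11-day gap between arms (day 10 v 21) is extreme. If the standard deviation were 2 points (an assumption), the standard error of a difference at 8 per arm would be 2 x sqrt(1/8 + 1/8) = 1.0 point, well above either shift in Step 2.

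Fourth, Section 6.3 also mentions changes in pain within subjects, which could use Visit 1 as the reference. That would help, but neither the reference score nor the window is specified. The section does not rank its analyses either, so the first-month mean should not be called the main one.

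**Conclusion.** The point holds for the first-month mean and the days 1-30 sub-analysis. As written, the surgery-based window puts at least the Visit 1 score, taken before PNS, into the outcome. The loss is modest on the reading closest to the specified data collection (6-10% of any effect), larger if only scheduled visits count (25%), and 31-44% at the upper bound. These shares assume PNS on day 6-7 and discharge on day 14; the 6% end uses day 21.

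Dependence on length of stay is conditional. It arises only if daily and weekly scores are averaged equally, and it is worth about 0.05-0.13 points for a 4-day difference in discharge under the assumed curves. It would bias the comparison only if discharge timing differed between arms.

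A reader might extend the criticism to the second-month mean because one sentence defines both. The visit calendar does not support that unless a stay passes day 30.

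In a pilot of 16 subjects with unadjusted p-values this does not threaten the trial. It does affect how far the acute-pain estimate can be used to plan the next one, and it is cheap to correct.

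**What to change.** Amend Section 6.3 as follows.

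1. Start the first-month and acute-phase windows after Visit 1 in both arms. Visit 1 exists in both groups, whereas PNS start does not.
2. Use the Visit 1 score as the baseline and leave it out of the outcome mean.
3. List the assessments that enter. Then either compute a time-weighted mean (area under the score-time curve divided by the number of days covered) or use one score per week in both arms.

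The data are already to be collected, so the cost is a few sentences and slightly more programming. The downside is that the summary no longer describes the whole first post-operative month; a descriptive surgery-based mean could be kept beside it.

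Two limits remain. Any days between Visit 1 and lead placement stay in the window. And BPI item 5 asks about the past week (Section 4.1.1), so its earliest on-treatment answers still cover days before PNS; items 3 and 4, with 24-hour recall, are much less exposed.

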Patients who are interested in participation will be asked to complete a Beck Depression Inventory (see Form BDI) to be screened for depression (must score 20 or less) prior to enrollment. Veteran participants who are evaluated by study staff and suspected to be depressed will be further evaluated by a psychiatrist or psychologist utilizing the Mental Health Consultation and Liaison Service at McGuire VAMC. Research study staff will page the C&L service at [name] (Use [name] after 4pm and on weekends) and then walk the participant to the C&L provider to facilitate the evaluation on the day that the participant

presents as depressed. If non-veterans participants are enrolled, arrangements made for him/her to be evaluated at a non-VA facility.

[figure not shown]

Figure 1 Subject flowchart.

258

259

260261

Patients who agree to participate in the study will be asked to sign the Consent Form. Ideally, patients should provide informed consent and be enrolled in the study prior to surgery. Typically, the local anesthetic peripheral nerve block catheters (or single shock femoral or sciatic nerve blockade) are placed on the day prior to surgery or day of surgery. Subjects will be given the opportunity to enroll in the study when the catheter is placed, however, those who wish to decide on enrollment after their surgery may be enrolled up until the time in which their peripheral nerve block catheter is removed, which is usually by post-op day 5. Upon enrollment, subjects will be evaluated by APS daily.

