The Consent Form will be scanned into the electronic medical record. Consent for photographic and video recordings will be requested. If collected, photographs and videos are intended for potential use in publications, future grant applications, and educational purposes. Subjects will receive a copy of their consent forms if requested. HIPPA Forms will be signed. The Schedule of Study Procedures outlines the baseline information and outcome measures recorded at each "Visit" on Case Report Forms (CRFs). All completed paper documents will be securely stored in a locked box placed in a fixed, locked file cabinet in the Interventional Pain Clinic on 2C. Only authorized study personnel will have the keys to access study materials containing protected patient information. A note may be documented in the patient's electronic medical record to indicate participation in the study. Subjects will be randomized to Group 1 ("Treatment Group") or Group 2 ("Control Group") (see Section 6.2. Sampling and Randomization Procedures).

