6.2 Sampling and Randomization Procedures

Based upon historical data on amputations at the HHM-VAMC, there are estimated to be one to two 474 475 amputations per week that would qualify for enrollment in this study. Subjects will be screened for enrollment through the vascular surgery clinic. A considerable proportion of vascular clinic patients will 476

require lower extremity amputation and are usually scheduled for next day surgery due to the urgency of 477

presentation. Study investigators will conduct a chart review of potential subjects and complete Form 01-478

479 A (screening and demographic information). Based on the chart review, if a patient appears to meet all 480

eligibility criteria, then they will be contacted by study investigators for potential enrollment. If the patient

agrees to participate, they will be consented and randomized to Group 1 or Group 2. 481

482 Prior to the start of this study, a member of the study staff that is not involved with recruitment or data

483 evaluation will be responsible for generating a random string of group assignments long enough to fill all

anticipated spots in this study. The numbers will be placed in secure envelopes by blocks of two. A block 484

485 of two will contain one assignment to the Treatment Group and one assignment to the Control Group. As

486 subjects are consented and enrolled in the study, they will be assigned an envelope which randomizes them

487 to a group. Subjects are not blinded to their group assignments. Subjects in the Treatment Group will

receive the investigational treatment (30 to 60-days of peripheral nerve stimulation) in addition to SMT. 488

489 Subjects in the Control Group will be treated with the SMT alone.

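### Section 6.3 tests both pain scores and pain changes by t-test with no reference visit for change, and does not use the Visit 1 baseline; a baseline-adjusted lead analysis is a cheap remedy if Visit 1 is recorded before allocation.

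*Combined protocol and SAP*

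**What the plan says.** Section 6.3 (Data Analysis) plans between-group comparisons of average, worst and least pain. The next sentence begins "Changes in pain will be evaluated for" and goes on to a between-group comparison of those changes. Means are formed for the first and second months after surgery, and sub-analyses look at "outcomes between groups over different post-operative phases (such as acute (e.g. days 1-30) or subacute" and chronic phases. The stated method is "Statistical analysis will be performed with two-sample t"-test, with unadjusted p-values, which the section justifies by the feasibility design. It names no visit from which change is measured and no covariate, and does not say which of the two comparisons leads.

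On the baseline, section 5.5 states: "The Schedule of Study Procedures outlines the baseline information and outcome measures recorded at each" visit. As far as the extracted table can be read, the Appendix labels Visit 1 as baseline and marks BPI #2, #3, #4 and #5 there, together with randomisation. Section 5.5.1 lists only BPI #2 and #5 at Visit 1.

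On the time of allocation, section 6.2 says that as "subjects are consented and enrolled in the study, they will be assigned an envelope which randomizes them" to a group. Section 5.5 says patients ideally "should provide informed consent and be enrolled in the study prior to surgery". Section 3.2 instead describes enrolment and randomisation of subjects with moderate pain 2 to 7 days after surgery. Section 6.2 adds: "Subjects are not blinded to their group assignments".

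**The concern.** Two estimates are planned for the same pain item in the same window, and nothing says which one is the answer. They differ by whatever pain difference the two groups happen to have at the reference visit. With 8 per arm that difference is often not small. Section 6.1 intends to report clinically significant group differences and to use the results to design a larger trial, so a reader could be handed two conflicting answers on one item.

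Three details bear on any use of Visit 1 as baseline:

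- **Allocation.** Under section 6.2 the group may be known before an open-label subject rates pain at Visit 1. Under the Appendix, randomisation happens at Visit 1.
- **Items.** If staff follow section 5.5.1, worst and least pain (BPI #3 and #4) have no baseline.
- **Overlap.** The first-month mean and the acute phase run from surgery, so Visit 1 and earlier scores can be counted in the outcome.

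**Working it through.** **Inputs from the documents.** 16 subjects, 8 per arm (section 6.1; 8 + 8 = 16). Two-sample t-test (section 6.3). The plan states no power, alpha, SD, effect size or dropout, so there is no sample-size calculation to reproduce.

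**Assumptions.** Two-sided 0.05; normal scores; equal SDs in the two arms; complete data; change = phase mean minus Visit 1. Baseline SD is set to 1. r is the correlation of Visit 1 with the phase mean, and k is the ratio of phase-mean SD to Visit 1 SD. The documents give neither, so r = 0 to 0.7 and k = 0.8 to 1.2 are shown.

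**Step 1: how far apart the two estimates are.** Score difference minus change difference = baseline difference. Its SD is sqrt(2/n) = sqrt(2/8) = 0.500. Its mean absolute size is 0.500 x sqrt(2/pi) = 0.40, and it exceeds 0.5 SD in 32% of trials. At 7 per arm the mean is 0.43 (35% of trials exceed 0.5 SD); at 6 per arm, 0.46 (39%).

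**Step 2: consequence for the tests.** Simulation with 200,000 trials per setting, 8 v 8. With no true effect, each t-test alone rejects in about 5%, at least one of the two rejects in 8.1-9.6%, and ANCOVA rejects in about 5%. With a true effect of 1 SD, exactly one of the two t-tests is significant in 26-47% of trials (34% at r = 0.5, k = 1). Low power contributes to that: it is about 46% for either t-test at r = 0.5, k = 1.

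**Step 3: what ANCOVA does.** Regressing the phase mean, or the change, on group and the Visit 1 score gives the same group estimate, so the choice between score and change disappears.

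**Step 4: its cost in precision.** Relative variances are: score k^2; change 1 + k^2 - 2rk; ANCOVA k^2(1 - r^2)(1 + 1/12). The 1/12 is the expected cost of estimating the slope, 1/(14 - 2). Critical values are t(14) = 2.145 and t(13) = 2.160. The CI-width ratio to the score test is (2.160/2.145) x sqrt((1 - r^2) x 13/12), whatever k is.

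| r | ANCOVA v score | v change, k = 0.8 | k = 1 | k = 1.2 |
|---|---|---|---|---|
| 0 | 1.048 | 0.655 | 0.741 | 0.805 |
| 0.3 | 1.000 | 0.743 | 0.845 | 0.915 |
| 0.5 | 0.908 | 0.793 | 0.908 | 0.978 |
| 0.7 | 0.749 | 0.831 | 0.967 | 1.031 |

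Break-even is r = 0.30 against scores, and r = 0.82 against change at k = 1. At r = 0 with 7 or 6 per arm, the CI is 5.9% or 7.7% wider than for scores.

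**Step 5: if Visit 1 is rated after the group is known.** Suppose knowledge of the group shifts reported baseline pain by d in one arm, with no effect on later pain. The score comparison moves by 0, change by d, and ANCOVA by about r x d (0.5d at r = 0.5, k = 1). For a hypothetical d = 0.5 SD, k = 1 and no true effect, rejection rates are:

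| r | score | ANCOVA | change |
|---|---|---|---|
| 0.5 | 5% | about 8% | about 16% |
| 0.7 | 5% | about 14% | about 23% |

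ANCOVA therefore holds its 5% level only with a baseline unaffected by allocation.

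**The case against.** The strongest case against acting is that this is a pilot with openly unadjusted p-values, that the t-test is valid, and that ANCOVA could do worse than the plain score comparison if section 6.2 is followed as written. The last part stands (Step 5) and makes the remedy conditional. It does not rescue the present plan, because the planned change comparison suffers more from the same shift than ANCOVA does. The pilot status lowers the weight of the p-values but does not settle which estimate is reported.

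Also standing: a subject without the Visit 1 item is lost to the ANCOVA unless imputed, and the size in Step 1 depends on change being taken from Visit 1, which section 6.3 does not say.

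A reader might infer several stronger things that the documents do not support:

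- *That the t-test is wrong.* It is not; randomisation justifies it.
- *That ANCOVA supplies a lead comparison for the trial.* Six measures (three BPI items, each for phantom and residual limb pain) by five windows (two monthly means, three phases) still leave 6 x 5 = 30 estimates, against 60 with both score and change.
- *That precision will improve.* No r is given. The one-week recall of BPI #5 can reach back into the nerve-block period, which could make r low.
- *That Visit 1 falls on day 6-7 for everyone.* Section 5.5 says only that the "peripheral nerve block catheter is removed, which is usually by post-op day 5". Section 5.5.1 sets Visit 1 at least 24-48 hours after removal, or after a single-shot block has worn off. Its timing varies with block type and removal date.
- *That other scales have the same conflict.* Section 6.3 plans only group averages for PDI and PCS and does not mention BPI #9. Section 4.2.6 already gives FIM a baseline and an improvement comparison.

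**Conclusion.** The concern holds in limited form. Section 6.3 leaves change undefined, plans two estimates per pain item and window with no rule between them, and leaves a scheduled baseline unused. The sizes in Steps 1 and 2 rest on 8 complete subjects per arm, normal scores, equal SDs between arms and change from Visit 1. Because the documents give no pain SD, a gap of 0.5 SD cannot be translated into points on the 0-10 scale or judged for clinical importance.

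Baseline adjustment is a worthwhile and inexpensive improvement only if Visit 1 pain is recorded before allocation is known. This is a change that should be made, not a flaw that invalidates the analysis.

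**What to change.** 1. **Prerequisites.** Reconcile section 6.2 with the Appendix on when randomisation occurs (section 3.2 should agree too), so that Visit 1 pain is recorded before the envelope is opened. Reconcile section 5.5.1 with the Appendix so that BPI #3, #4 and #5 are all collected at Visit 1.
2. **Reference.** In section 6.3, name Visit 1 as the reference for change, and leave Visit 1 and earlier scores out of the phase means.
3. **Lead analysis, conditional.** If Visit 1 precedes allocation, make the lead analysis of each pain item in each phase an ANCOVA of the phase-mean score on the same item at Visit 1. Report the adjusted difference with its 95% CI and keep the t-test as a sensitivity analysis. If Visit 1 follows allocation, let the comparison of phase-mean scores lead, and use neither change nor ANCOVA as lead.
4. **Missing Visit 1 items.** State in advance how they are handled.

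Baseline adjustment of PDI, PCS, FIM and BPI #9 is optional. Choosing a lead item and window for the trial is a separate decision that this change does not make.

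The cost is plan wording, a little programming, holding the envelope until Visit 1 pain is scored, and one degree of freedom. No new patients are needed, and no new data if the Appendix schedule is followed.
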